

Study Design

Design

We will use a random number generator to assign study participants to one of 2 conditions: 1) usual care (control); or 2) behavioral economic intervention. The research team will create the randomization list and a research assistant will assign the participant to the correct online platform condition, but the investigators and data analysts will remain blind to group assignment. This study will contain two parallel groups. Although participants will not initially be aware of the other study condition, they will not be blinded to study condition because those in the intervention condition will be viewing the altered ordering platform as they shop.

Study duration

This study is estimated to take four years. Year 1 will be spent finalizing the research protocol, updating the food pantry web-platform, categorizing pantry food with traffic lights, and hiring and training study staff. We will begin recruiting participants and collecting data in the second half of year 1. Subjects' participation will be for four months (one month pre-baseline, three months post-baseline). Participant recruitment will continue through years 2 and 3 of the study and data collection will continue through years 2, 3 and the first half of year 4. Year 4 will be spent cleaning and analyzing data and preparing manuscripts.

Characteristics of the Study Population

Target population

We will aim to recruit 500 individuals (only one per household) who regularly shop at the Jewish Federation food pantry in Philadelphia, PA. We have complete data for 61 participants at the 3-month post-intervention assessment point as of the end of 2020, and we will aim to recruit 439 more participants. Based on demographic data from the previous year, we expect approximately 55% of pantry customers will be women and the racial breakdown will be as follows: 78.5% White, 12.3% Black, 7.8% Asian, 0.1% Native Hawaiian or Other Pacific Islander, 0.5% more than one race, and 0.8% unknown race. We anticipate 1% of the sample to identify as Hispanic. In general, this is largely a very-low income, older, immigrant population. The majority (60%) of these individuals use SNAP benefits.

Subjects enrolled by Penn Researchers

500

Subjects enrolled by Collaborating Researchers

0

Vulnerable Populations

Children Form

Pregnant women (if the study procedures may affect the condition of the pregnant woman or fetus) Form

Fetuses and/or Neonates Form

Prisoners Form

Other

None of the above populations are included in the research study

The following documents are currently attached to this item:

There are no documents attached for this item.

Subject recruitment

Participants will be recruited on-site at the pantry and remotely by study staff working closely with food pantry staff. Recruitment posters will be displayed at the pantry and recruitment post cards will be provided to food pantry clients. All study materials will be branded with a name and logo so that it is recognizable to participants. We will have all study documents available in the most common languages spoken by food pantry clients (English and Russian) and food pantry staff and study staff who speak these languages will be available to translate and discuss study procedures with clients. Our pantry partners have strong relationships with their clients, are highly invested in this study, and believe we will have no trouble meeting our target goal of 500 individuals out of the nearly 2600 that regularly visit the pantry.

Ukrainian translation was not done because we learned from the food pantry staff and our conversations with clients that the clients are largely English or Russian speaking and do not need Ukrainian language materials. Furthermore, the online ordering system at the food pantry is only available in English or Russian, so all clients shopping there must be able to communicate in one of those two languages. Finally, no clients to date have requested Ukrainian materials.

Attachments:

[fp_PostCards Recruitment_EN_v1.0_2020-12-14.pdf](#) (English post card)

[fp_PostCards Recruitment_RU_v1.0_2020-12-14.pdf](#) (Russian post card)

[fp_Translation for UPenn_RU_2020-12-14.pdf](#) (Certified Translation of PostCards Recruitment 2020-10-06_EN.pdf)

[fp_Poster_EN_v1.0_2020-12-14.pdf](#) (English poster, Certified Russian Translation to be included in subsequent modification)

Will the recruitment plan propose to use any Penn media services (communications, marketing, etc.) for outreach via social media avenues (examples include: Facebook, Twitter, blogging, texting, etc.) or does the study team plan to directly use social media to recruit for the research?

No

The following documents are currently attached to this item:

There are no documents attached for this item.

Subject compensation*

Will subjects be financially compensated for their participation?

Yes

The following documents are currently attached to this item:

There are no documents attached for this item.

If there is subject compensation, provide the schedule for compensation per study visit or session and total amount for entire participation, either as text or separate document

Prior to the COVID-19 pandemic, the study was conducted with three assessment points at baseline, 3-months, and 12-months. Since the pandemic, we have changed study protocols to only conduct assessments at baseline and 3-months. Participants who were enrolled prior to the pandemic who have not reached the 12-month time point have been notified that there will be no data collection at 12 months. For completing the assessments at baseline and 3-months, we will compensate participants \$25 for each visit. This incentive will be broken up into the following payments: \$10 for surveys, \$5 for blood pressure measurement, \$5 for weight measurement, and \$5 for veggie meter

(diet quality) measurement. We will also remunerate participants \$25 for completing a training on how to use the pantry online ordering system. Participants will be paid via ClinCards. These are debit cards that we have successfully used in other longitudinal research studies that enable us to automatically load money onto a participants' card, which they can then use at any store like a debit card. We will also approve Check payments for participants who are unable to receive ClinCards. To strengthen cohort retention, we will incentivize successful online shopping each of the three months that participants are in the study after baseline measurements. For completing their baseline order, participants will receive a \$5 payment, for months 1 and 2, participants will receive \$3, and for month 3, participants will receive \$4, totaling \$15 for all orders. The total financial compensation for participation is \$90 (\$25 + \$25 + \$25 + \$15).

Prior to the COVID-19 pandemic, we planned to strengthen cohort retention during the study by entering each participant into several lotteries where 10 people had the chance of winning \$5 prizes and one person would win a \$100 prize. Because of the shortened timeline of the study (1 year to 3-months), we will no longer use a lottery to encourage cohort retention. We also planned to provide a \$3 incentive twice for participants confirming their contact information at 3-months and 12-months. Because of the shortened study timeline and that we will now incentivize shopping monthly, we will no longer provide a \$3 incentive for confirming contact information.

Study Procedures

Suicidal Ideation and Behavior

Does this research qualify as a clinical investigation that will utilize a test article (ie- drug or biological) which may carry a potential for central nervous system (CNS) effect(s)?

No

Procedures

In response to the COVID-19 pandemic, on March 11, 2020, the Mitzvah Food Program at the KleinLife Community Center (where our research study takes place) changed their food order and pick up protocol. No clients are allowed to enter the facility and instead must either order online remotely (maintaining choice selection) or choose a pre-packaged bag that is picked up outside at the door. Study procedures before the start of the COVID-19 pandemic involved participants placing food orders in-person at the food pantry and study staff conducting physical measurements and surveys with participants in-person at the food pantry. These study procedures are detailed below under "Pre-COVID-19 Procedures." Since the start of the pandemic, we have adapted our study procedures to ensure safety for participants and study staff. These new study procedures are as follows.

Participants will be recruited on-site at the Jewish Federation of Greater Philadelphia Food Pantry or remotely by study staff working closely with food pantry staff, following all current COVID-19 safety guidelines. We anticipate that the eventual availability of a vaccine will allow recruitment either remotely or on-site. We will ask participants several screening questions to determine their eligibility. Eligible participants will meet the following criteria:

- 1) At least 18 years old;
- 2) Regularly shops at the food pantry (at least once per month)
- 3) Primary food shopper for household (Only one member of household can participate)
- 4) Willing and able to place orders themselves or with assistance (while still viewing the screen) using the online ordering system
- 5) Willing and able to use a blood pressure cuff and scale provided to them for taking blood pressure and weight.
- 6) We have added the fourth screening criterion to ensure that participants will place online orders even if the pantry is operating remotely. After determining eligibility, we will administer informed consent electronically using the REDCap electronic-consent (e-consent) framework, detailed in the informed consent section of this protocol. We will offer to read the consent form and talk through the process with participants, and we will provide the option of paper consent forms for any participants not comfortable with the electronic consent process.

As part of the informed consent process, participants will be asked whether they would like to be contacted about future opportunities to participate in other research studies. Their response will be documented on the informed consent form (either on REDCap or a paper form). If they answer affirmatively, their name, e-mail, and phone number will be added to a REDCap database separate from this project and will be used for recruitment for studies within the PEACH Lab at the University of Pennsylvania. This database will not be shared with anyone outside of the Lab.

After consenting to participate, we will collect basic contact and demographic data consisting of the following elements: name, date of birth, address, phone number, email address, language, race, ethnicity, education level, gender, children living in household, and cigarette smoking behavior.

We will conduct study assessments with participants at two time points: baseline and 3-months post intervention. We will conduct baseline measurements of height, weight, blood pressure, and diet quality using the Veggie Meter with participants at their homes or at the food pantry following all current COVID-19 safety guidelines. We will use a script to describe measurements when calling participants to schedule their measurement appointments (fp_Script to describe measurements to participants). To aid with contactless measurements, we will provide participants with printed instructions (fp_Measurement Instructions for Participant, fp_Veggie Meter Instructions for Participant).

These documents have been professionally translated

We will administer diet and health surveys (fp_DietSurvey, fp_HealthSurvey) electronically through REDCap surveys. We will provide the option of doing surveys over the phone on an as-needed basis for participants not comfortable with electronic surveys.

Participants will receive \$25 for completing all components of baseline measurements (\$10 for surveys, \$5 for blood pressure, \$5 for weight, and \$5 for veggie meter). We will provide participants with their blood pressure and weight results at the time of measurement using printed cards (fp_Results Cards). We will provide weight and blood pressure results only and not BMI or Veggie Meter results as these are not meaningful results for participants. Blood pressure results include a desirable range from low to high blood pressure, and direct participants to consult with their doctor if results are outside this range.(1)

Following baseline measurements, participants will be randomized to one of two conditions: 1) the usual care group (control); or 2) the behavioral economic intervention.

To encourage participants to place orders using the food pantry's SmartChoice online ordering system, we will incentivize shopping by paying participants for successfully placing each order. We will train research participants on how to use the SmartChoice system via a walkthrough with study staff prior to their first order, for which they will be remunerated \$25. Participants will be remunerated for each order as follows: \$5 for baseline, \$3 for the first two months of participation, and \$4 for the third month of participation. We will provide printed online order guides to support online ordering (fp_Online Order Guide). We will also offer four months of contactless food delivery. Contactless means that when the Research Assistant brings the food to the study participant's home, they will place the food at the door, knock or ring the doorbell, and wait at a safe distance as the participant picks up the food. We will use phone and text messaging through Mosio, a secure text messaging platform, to communicate with participants using text message templates (fp_Text_Message_Templates).

Deliveries will only be offered to those participating in the study remotely, and for that reason we have removed any information about deliveries in our informed consent forms.

Three months after baseline, we will conduct 3-month measurements of weight, blood pressure, and diet quality using the Veggie Meter with participants at their homes or at the food pantry following all current COVID-19 safety guidelines. We will administer the diet survey again electronically through a REDCap survey. We will not administer the health survey at 3-months. We will provide the option of doing the survey over the phone on an as-needed basis for participants not comfortable with electronic surveys. Participants will receive \$25 for completing all components of 3-month measurements (\$10 for the survey, \$5 for blood pressure, \$5 for weight, and \$5 for veggie meter). We will provide participants with their blood pressure and weight results at the time of measurement using printed cards.

Food delivery will end after four months. We will use a post flyer to inform participants of their last food delivery (fp_PostCards Last Delivery).

After completing all study components, we will use a questionnaire (fp_Post-Study Questions) to ask participants a series of questions about their perceptions of the intervention, provide a short debriefing about study, and then ask whether or not they prefer to keep or remove the intervention depending on the condition they were assigned to.

If we are unable to reach a participant by phone after three attempts at any point throughout the study, we will mail them a letter asking them to contact us (fp_FoodPantryContactInfoFollowUpLetter).

Clean and track-changes Microsoft Word copies of this protocol are attached here (fp_FoodPantryIRBProtocol).

Staff Training and Protections

All study staff will complete HIPAA, GCP, CITI, and safe driving trainings before implementing this protocol. Study staff will use masks, practice social distancing, and use hand sanitizer and wash hands frequently.

Food pickups and deliveries and physical measurements will be contactless for as long as is required by University and government safety guidelines. Blood pressure cuffs, monitors, and scales are considered noncritical surfaces in health care because they only touch intact skin, and we will follow the recommendation to disinfect between each participant use.(2)

To ensure food safety, we will use cooler bags to store refrigerated and frozen items and make sure food is not in transport for long periods of time.

References

1. National Heart, Lung, and Blood Institute. Low Blood Pressure. National Institutes of Health, United States Department of Health and Human Services. <https://www.nhlbi.nih.gov/health-topics/low-blood-pressure>. Accessed December 14, 2020.
2. Havill NL. Best practices in disinfection of noncritical surfaces in the health care setting: Creating a bundle for success. Am J Infect Control. 2013;41(5 Suppl):S26-S30.

Pre-COVID-19 Procedures

Participants will be allowed to visit the pantry at their normally scheduled time to allow for convenience for the participant. During each visit, participants will order their grocery items using the web-based touchscreen system. The web-based ordering platform at the food pantry, will enable us to easily capture and evaluate all food selections at the pantry over one year per participant. Once orders are placed, a receipt is printed out and food pantry staff fill the order. Before participants place their order, study staff will measure participant weight, height, and blood pressure in a private room, which is estimated to take approximately 5 minutes. To ensure standardized weights over time, trained research assistants will follow a clear protocol (participants will be instructed to wear light clothing, no shoes for weighing, and each participant will be weighed twice on a digital scale). Height will also be assessed to the nearest 1/8 inch using a stadiometer. Participants will then be given the Block Food Frequency Screener in order to measure their fruit and vegetable intake. The screener includes questions about usual fruit and vegetable intake and takes about 5 minutes to complete. Participants were then given a health questionnaire. Participants will have their dermal carotenoid levels measured with a Veggie Meter, a non-invasive device which uses reflection spectroscopy to measure the pigment in the skin which corresponds to fruit and vegetable intake.

Originally, after attending the food distribution at each time point, participants were instructed to visit a nearby LabCorp to complete a blood draw that measured a fruit and vegetable biomarker (beta carotene serum levels) and HbA1c. Blood measurements will also include a lipid panel (total cholesterol, LDL, HDL, triglycerides, and glucose), c-reactive protein, and serum glucose. However, this proved unreliable and burdensome, so the lab tests were eliminated and replaced by the aforementioned dermal carotenoid measurement in October 2019. This did not change the incentive structure. Those who were previously offered LabCorp appointments were given the opportunity to continue going if they so chose, but were not required to have blood work done for study participation.

The following documents are currently attached to this item:

There are no documents attached for this item.

Deception

Does your project use deception?

No

International Research

Are you conducting research outside of the United States?

No

Analysis Plan

Data will be descriptively summarized and evaluated for quality prior to the evaluation of primary and secondary endpoints. Means and standard deviations will be used to characterize continuous variables such as weight and blood pressure, and frequencies and percentages will be used to describe categorical variables such as nutritional quality. Medians and interquartile ranges will be reported for continuous variables that exhibit skewness. Data will be descriptively summarized overall and by condition. All outcomes will be analyzed at the customer level except for nutritional quality, which will be analyzed at the item level. Analyses will employ population-averaged marginal models estimated by Generalized Estimating Equations (GEE) to account for correlations among longitudinal monthly measurements and items purchased per food pantry customer. Marginal models estimated by GEE are advantageous for their population-level interpretation and robustness of estimated effects to the assumed correlation structure among repeated measurements (meaning unbiased estimates of the effect of the behavioral economic intervention will be obtained whether or not the correlation among repeated measurements within a food pantry customer is modeled correctly). Clusters will be defined at the level of the customer for all analyses, and independence working correlation will be assumed. Linear models will be used for continuous outcomes and logistic models for ordinal outcomes such as nutritional quality. Models will include 2-level intervention, month, and the interaction of intervention and month as categorical variables. The primary analysis of testing the effectiveness of the behavioral economic arm compared to the control arm will be evaluated by the joint test of the null hypothesis test that intervention-month interaction coefficients are 0, denoting no difference in the change in respective outcomes from baseline to month 3 between intervention groups. Secondary analyses will test for changes in intervention effects over time by testing whether intervention-month interaction coefficients are equivalent at month 3. We will evaluate the sensitivity of estimated intervention effects to imbalances in baseline covariates and missing data. To assess the impact of imbalance in baseline covariates, outcomes will be reanalyzed in models that adjust for baseline covariates that differ significantly at the 0.05 level by intervention arm. We will evaluate sensitivity to missing data by inverse probability of weighted GEE and multiple imputation. The Holm procedure⁷⁷ at a family-wise error rate of 0.05 will be used to account for multiple comparisons in testing differences in five primary outcomes between the two groups (nutritional quality of food selected, fruit and vegetable intake based on the food frequency questionnaire, weight, and blood pressure). Similar analyses of dermal carotenoids will be performed as secondary endpoint analyses.

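### The 500 combines 61 earlier completers with 439 recruits under changed procedures, but the models have no period term and no by-period result is planned

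*Combined protocol and SAP*

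**What the plan says.** Under Target population the protocol states "We have complete data for 61 participants at the 3-month post-intervention assessment point as of the end of 2020", and then that "we will aim to recruit 439 more participants". The two figures make up a single sample of 500.

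The Procedures section dates the change in pantry operation to 11 March 2020. It describes the earlier conduct as "participants placing food orders in-person at the food pantry and study staff conducting physical measurements and surveys with participants in-person at the food pantry". On eligibility it says "We have added the fourth screening criterion to ensure that participants will place online orders even if the pantry is operating remotely". The next criterion in the list requires participants to be able to use a supplied cuff and scale.

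Under Pre-COVID-19 Procedures, participants ordered on a touchscreen at the pantry and staff took the measurements; for weight, "each participant will be weighed twice on a digital scale". Under the current procedures:
- recruitment may be on-site or remote;
- measurement may be at home or at the pantry;
- surveys are electronic, with a telephone option;
- ordering training and each monthly order are paid;
- participants taking part remotely are offered food delivery.

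Study Design describes assignment by random number generator and states no stratification. The Analysis Plan says "Models will include 2-level intervention, month, and the interaction of intervention and month as categorical variables". Covariate adjustment appears only as a sensitivity analysis, for baseline covariates that differ between arms at the 0.05 level. Enrolment period is not mentioned there.

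**The concern.** Participants enrolled before and after the change may differ in who could enter, where they saw the nudges, how weight and blood pressure were taken, and what kept them ordering. Their average change from baseline to month 3 may therefore differ for reasons unrelated to the intervention. With no period term, that difference stays in the residual variation.

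Interpretation is also affected. The pooled estimate averages over ordering at the pantry and ordering that may take place at home, and nothing in the plan would show whether the smaller, earlier group points the same way as the larger one. If the question comes up only after unblinding, any decision about the earlier participants will look post hoc.

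**Working it through.** **The plan's own figure.** 61 + 439 = 500, so the stated total is reproduced as a sum. The documents give no effect size, standard deviation, power or dropout rate, so 500 cannot be checked as a powered sample size. The earlier share is p = 61/500 = 0.122 and the later share 0.878.

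**Who the 61 are.** No enrolment dates are given. Month-3 data by 31 December 2020 implies a baseline by about the end of September 2020. The new recruitment materials listed under Subject recruitment carry dates from 6 October to 14 December 2020. The Subject compensation text confirms that some participants enrolled before the pandemic. It is therefore likely, but not stated, that most of the 61 came in under the older procedures. All 61 are treated as earlier below.

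**Assumptions.** 1:1 allocation (the ratio is not stated), outcome change with within-period SD 1, normal approximation, and d = difference between periods in mean 3-month change, in SD units. The documents give no value for d, so a range is shown.

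**Precision lost.** Variance of change without a period term = 1 + p(1 − p)d² = 1 + 0.122 × 0.878 × d² = 1 + 0.107d². The power column is for a true effect of 0.25 SD at two-sided 0.05; with no inflation it is 79.8%.

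| d | Variance increase | Effective N (500 / inflation) | Power |
|---|---|---|---|
| 0.25 | 0.7% | 497 | 79.6% |
| 0.5 | 2.7% | 487 | 78.8% |
| 1 | 10.7% | 452 | 75.7% |

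**Chance imbalance is the same quantity.** Under simple randomization the SD of the between-arm difference in earlier share is 2 × √(0.107/500) = 0.0293. The 95% chance shift in the effect is 1.96 × 0.0293 × d = 0.057d SD. The standard error of the arm comparison is √(4/500) = 0.089 SD, so the shift at d = 1 is 0.057/0.089 = 0.64 standard errors. Squaring, 0.0293²/0.008 = 0.107, which is the variance inflation already counted. It must not be added again.

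**Averaging of effects.** If the true effect were 0.25 SD in the later 439 and zero in the earlier 61, the pooled effect would be 0.878 × 0.25 = 0.22 SD.

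**What a by-period comparison can show.** SE of the arm-by-period contrast = 2 × √(1/61 + 1/439) = 0.273 SD. The difference detectable with 80% power is (1.96 + 0.84) × 0.273 ≈ 0.77 SD. Power is 15% for a difference of 0.25 SD and 45% for 0.5 SD. A formal interaction test would be close to uninformative.

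**Which term matters.** The primary test concerns change from baseline. In the linear models with complete data, a period main effect shifts both visits equally and drops out of the arm-by-month coefficient. Only a period-by-month term removes a period difference in change.

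**The case against.** The strongest reply is that randomization already protects the comparison. A reader might infer that pooling the two periods biases the treatment effect. The documents do not support that: participants are randomized after baseline, and nothing suggests that allocation differed by period. A constant offset from the way weight or blood pressure was taken also cancels within a person measured the same way at both visits. At d of 0.25 to 0.5 the loss of precision is trivial, and nothing in the documents makes d = 1 likely. All of this stands.

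The contrast between periods can also be drawn too sharply:
- Food selections come from web-platform transaction data in both periods, so nutritional quality, the first-listed primary outcome, is not measured differently.
- Later recruits are not all remote. They may be recruited or measured at the pantry, and delivery is only for those taking part remotely.
- The text says only that the fourth criterion was added. That the cuff-and-scale criterion was also new is an inference from its fit with contactless measurement.

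The planned covariate sensitivity analysis does not close the gap. It does not name period, and under randomization a 0.05 test would select period only about one time in twenty. If it entered only as a main effect, it would leave the change comparison in the linear models as it was.

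**Conclusion.** The point holds as a matter of precision and reporting; it does not threaten validity. The pooling, the changed procedures and the absent term are all in the text. The arm-by-month test is not biased in expectation. The cost is a variance increase of 0.107d², or 0.7% to 2.7% for d between 0.25 and 0.5 and 10.7% at d = 1, with chance imbalance already included. The larger practical loss is that no planned result shows whether the earlier 12% agrees with the rest.

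This rests on 1:1 allocation, on an assumed d, and on treating all 61 as earlier enrolees. If some of the 61 enrolled under the new procedures, the share and the inflation are smaller. The variance figures apply to the continuous outcomes; the item-level logistic analysis of nutritional quality would need its own calculation.

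**What to change.** Before unblinding, amend the Analysis Plan as follows:

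1. Define period from the criteria and procedures recorded for each participant at enrolment. Flag anyone whose baseline and month-3 visits fall on either side of 11 March 2020, since their measurement or ordering mode may have changed between visits.
2. Add period and period-by-month to the primary models. A period main effect alone is not enough in the linear models.
3. Report the arm effect with its confidence interval by period, labelled descriptive. Do not attach a formal interaction test, and do not let this comparison alter the main conclusion: with 61 people in one group, noise could produce an apparent difference.

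Stratifying the remaining randomization by period would achieve nothing, because every further recruit belongs to the later period.

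The cost is plan wording and one variable derived from enrolment records. The added terms use two degrees of freedom for outcomes measured at baseline and month 3 (one for period, one for period-by-month), and four for monthly outcomes with a baseline and three later months (1 + 3). Both are negligible at 500. The earlier-period estimate will be imprecise: its standard error is about 2/√61 = 0.26 SD. In the logistic model the odds ratio becomes conditional on period and will differ slightly from the marginal one, which the plan should acknowledge.
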